Currently, the hospital standard of care for glucose monitoring in diabetic patients is POC capillary blood glucose measurement performed usually before meals and at bedtime. This approach however only provides limited glucose measurements throughout the day and fails to detect nocturnal or asymptomatic hypoglycemia or hyperglycemia episodes, all of which are common insulin therapy complications. Continuous Glucose Monitors (CGM), a newly introduced technology, represent an alternative to this standard of care, with the potential to assist making personalized therapy decisions. CGMs measure and record levels of subcutaneous interstitial glucose every 5 minutes. The subcutaneous glucose measured by most recent CGMs closely mirror the capillary blood glucose levels. This continuous monitoring allows for better assessment of nocturnal or asymptomatic hypoglycemia or hyperglycemia, and shows glycemic patterns following treatment interventions. This monitoring allows for timely interventions, and was shown to reduce hyperglycemia and hypoglycemia episodes. Recent studies have demonstrated improved glycemic control in insulin-treated DM patients using

CGM in outpatient setting. FDA has approved these devices in outpatient setting for glucose monitoring and for dosing of insulin injection even without capillary blood glucose confirmation. In the outpatient setting these devices have become standard of care for both type 1 and type 2 diabetes management. Their use in inpatient setting is limited, and at this time it is not FDA approved. Concerns for reading accuracy in case of rapidly fluctuating clinical parameters, hypoxemia, tissue hypoperfusion and IV medications use have prevented the approval of these devices in inpatient setting. Still, when evaluated in hospitalized patients, small studies have found that CGMs are accurate and they can detect more episodes of hypo and hyperglycemia than POC glucometers, especially between meals and at night time.

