During the first 24 hours, sensor accuracy will be assessed. Patients will continue to have their blood glucose checked with POC glucometer concomitant with CGM use. CGM readings will be recorded in chart at the same time as POC glucometer reading is obtained. The glucometer readings and CGM data at the time of glucometer readings will be compared by nursing staff. The CGM readings should not be either 15% higher or 15% lower than the corresponding POC glucometer reading. Should this CGM reading fall outside this range, a second reading will be done within 30 minutes and readings will be compared to reassess accuracy. After the patient has had sensor in place for 24 hours and at least 4 POC glucometer glucose checks have been recorded and compared against CGM values and found to fall within the above range, the research team will be notified to determine if the frequency of POC checks can be safely decreased based on CGM accuracy.

If 2 or more consecutive CGM readings do not correlate with POC glucometer values, the research team will be notified. The research team will evaluate the data and decide if the sensor should be replaced and another 24-hour cycle of adjustment phase re-initiated, or if patient participation should be terminated. Only POC glucometer readings will be used to make decision about insulin dosing and administration during this phase. When charting insulin

administration, nursing staff will manually enter the CGM readings obtained at the time of insulin administration into the chart under the “comments” on the MAR screen.

If 4 comparison points – CGM readings and POC glucometer reading – are deemed accurate (within +/- 15% of each other for all 4 readings), then patient will enter the “Utilization Phase”.

Utilization Phase

During this phase, once the research team has confirmed CGM accuracy, POC glucometer AND CGM readings will be used to make decisions about insulin dosing and administration. The use of POC glucometer will be decreased as follows:

1. POC glucometer checks will be reduced from 4 times per day (qAC and QHS) to twice per day before breakfast and at bedtime (qAM and qHS)
2. Subcutaneous insulin dose for breakfast and bedtime will be determined based on POC readings
3. Subcutaneous insulin dose for lunch and dinner will be determined based on CGM readings
4. Nursing staff will continue to record CGM readings at the time of every insulin administration in the chart under the “comments” section on the MAR

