CGM data will be compared with POC blood glucose monitoring obtained in the hospital. Different patient variables (demographics, comorbidities, labs and vitals, administered medications) will be collected from electronic health record and will be evaluated to determine if they would interfere with CGM readings. The accuracy of CGM for glucose measurement in the hospital will be calculated.

At the time of discharge or after discharge patients will be contacted by research team and administered a survey regarding satisfaction with inpatient care and satisfaction with DM care.

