The study will use data that have been collected under another IRB protocol. Include in the Methods section and enter the IRB number from which the research material will be obtained. *When appropriate, note when subjects have provided consent for future use of their data and/or specimens as described in this protocol.*

Enter one IRB number per line, add more lines as needed

Data Specimens Data & Specimens _____

Data Specimens Data & Specimens _____

Data Specimens Data & Specimens _____

Data Analysis

Power Statement:

This a pilot study to demonstrate feasibility of CGM use in COVID patients and to determine if a subsequent more extensive implementation and studying of this device will be warranted.

Data Analysis Plan:

Data will be described as percentages or means. Pearson χ^2 and Kruskal Wallis tests will be used to compare categorical and continuous variables respectively. Odds ratios, 95% confidence intervals and p-values will be reported for each model. All tests of significance will be 2-sided and the level of statistical significance will be set at p-value < 0.05 .

Mean Absolute Relative Differences will be calculated between matched pairs of POC monitors and the closest CGM reading (within 5 minutes of POC). Additionally, level of agreement between the two devices will be examined with Bland-Altman plots, with particular attention focused on detection agreement in range (70-180 g/dl). Poisson or negative binomial regression will be utilized to assess count variables such as number of alarms, nurse notification, and hypo or hyperglycemia events adjusting for patient characteristics. Finally, longitudinal analysis will be conducted to determine differences associated with medications, clinical parameters or diagnosis. Analysis will seek to define if there are any differences between CGM and POC measurement based on these changes.

Endpoints

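### Scheduled SQ pairs leave the night and the hours after meals unsampled, and a single pooled MARD neither shows this nor separates CGM-triggered checks

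*Combined protocol and SAP*

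**What the plan says.** The Background describes usual care as "POC capillary blood glucose measurement performed usually before meals and at bedtime". It supports CGM partly by earlier small studies in which "they can detect more episodes of hypo and hyperglycemia than POC glucometers, especially between meals and at night time".

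In the SQ Adjustment Phase this checking pattern carries on: "Patients will continue to have their blood glucose checked with POC glucometer concomitant with CGM use". At least 4 comparisons are needed over 24 hours. In the SQ Utilization Phase, "POC glucometer checks will be reduced from 4 times per day (qAC and QHS) to twice per day before breakfast and at bedtime", and "Subcutaneous insulin dose for lunch and dinner will be determined based on CGM readings".

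The Data Analysis Plan builds MARD from "matched pairs of POC monitors and the closest CGM reading (within 5 minutes of POC". The Endpoints section lists MARD as a primary endpoint. Its secondary MARD analyses split by glucose level only. Nothing splits MARD by time of day, insulin route or reason for the check.

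Patients on IV insulin follow another schedule: hourly POC checks for 12 hours, then every 2 hours, returning to hourly when the CGM is outside 140-180 mg/dl or the infusion is adjusted.

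**The concern.** Aim 1 asks whether CGM is accurate enough for glucose monitoring in these patients, and the hypothesis would use a favourable answer to cut POC checks. An accuracy estimate speaks only for the times at which the reference was taken. In SQ patients those times are set by the meal and bedtime routine, while part of the case for CGM rests on the night and the hours between meals.

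Two features make one pooled figure hard to read. First, SQ pairs outside the routine arise largely because the CGM itself raised an alarm. Second, the hours that SQ patients leave empty are filled by IV patients, who are on a continuous infusion with a narrow range. A reader of the single MARD could not tell which hours, which patients or which kind of check it describes.

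**Working it through.** The plan has no calculation on this point to reproduce, so the check is a map of coverage followed by a count of scheduled pairs.

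**1. Scheduled coverage** (SQ and IV schedules in the Methods; a pair requires a POC reading)

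| Time | SQ Adjustment | SQ Utilization | IV insulin |
|---|---|---|---|
| Before breakfast | yes | yes | yes |
| Before lunch, before dinner | yes | no | yes |
| Bedtime | yes | yes | yes |
| Timed to follow a meal | no | no | covered by hourly or 2-hourly checks |
| Overnight | no | no | covered by hourly or 2-hourly checks |

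The documents give no ward times. If bedtime checks are at 21:00-22:00 and breakfast at 07:00-08:00 (assumption), the empty stretch is 9 hours (22:00 to 07:00) to 11 hours (21:00 to 08:00). That is 9/24 = 38% to 11/24 = 46% of the day.

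**2. Scheduled pairs per patient over d days.** Assumptions: wear of 3 to 10 days, one insulin route throughout, and Adjustment passed at the first attempt. IV patients are taken as always in range, so the IV count is a minimum.

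- SQ: 4 + 2 × (d − 1)
- IV: 12 + (24d − 12)/2
- SQ lunch and dinner doses guided by CGM with no scheduled pair: 2 × (d − 1)

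| d | SQ pairs | IV pairs | IV/SQ | Unpaired lunch and dinner doses |
|---|---|---|---|---|
| 3 | 8 | 42 | 5.3 | 4 |
| 5 | 12 | 66 | 5.5 | 8 |
| 7 | 16 | 90 | 5.6 | 12 |
| 10 | 22 | 126 | 5.7 | 18 |

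**3. Weight of IV patients in a pooled MARD.** The target accrual is 20 and no split by route is given. With k IV patients and each pair weighted equally (assumption), the IV share is k × IV / [(20 − k) × SQ + k × IV]. For k = 2 and d = 3: 84 / (18 × 8 + 84) = 84/228 = 37%. For k = 2 and d = 10: 252 / (18 × 22 + 252) = 252/648 = 39%. Taking 8/24 of IV checks as night checks (assumption):

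| IV patients of 20 | IV share of scheduled pairs | Night pairs, all from IV patients |
|---|---|---|
| 0 | 0% | 0% |
| 1 | 22-23% | 7-8% |
| 2 | 37-39% | 12-13% |
| 5 | 64-66% | 21-22% |
| 10 | 84-85% | 28% |

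If MARD were averaged within patients first, 2 IV patients would weigh 2/20 = 10%. They would still supply every scheduled night pair.

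**4. Selection of the off-schedule pairs.** In SQ patients a CGM value below 85 mg/dl leads to a POC check at any hour, with rechecks after treatment. If the CGM reads 85 or above while blood glucose is below 70, no alarm sounds and no pair is formed unless a check happens to be due. Alarm pairs can therefore reveal false lows but not missed lows. Sustained readings above 250 mg/dl lead to a POC check only if a provider asks for one. In Adjustment, a pair outside ±15% is repeated within 30 minutes, so it is selected on disagreement. Some IV Utilization pairs are also CGM-triggered: the immediate check on an alarm, and the return to hourly checks when the CGM leaves 140-180 mg/dl.

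**The case against.** The strongest reply is that the planned MARD is not confined to SQ patients or scheduled checks. IV patients are tested round the clock, and SQ patients can be tested at any hour on an alarm. Usual care is described only as usually following the meal and bedtime pattern, and Adjustment sets a minimum of 4 checks, so other ordered checks are possible. The bedtime check also comes after dinner, perhaps within a few hours. All of this stands. A reader might infer that MARD as a whole says nothing about nights or the hours after meals. The documents do not support that unless no patient is on IV insulin and no off-schedule check occurs.

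A reader might also infer that MARD will be flattering because the routine times are steadier. The documents give no sensor lag, rate of glucose change or comparison of routine with other hours, so neither direction nor size can be claimed.

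The plan does include MARD by glucose level and a longitudinal analysis by medication and clinical parameters, which could take in insulin route. Neither names clock period or reason for the check, so neither supplies the missing split. SQ low alarms are confirmed by POC, which guards against acting on a false low but gives no information on lows that raise no alarm.

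Finally, this is a 20-patient feasibility pilot, and Aim 1 does not single out night accuracy. That limits how much weight the point carries. It does not remove it, because the pilot is meant to inform whether wider use and study are warranted.

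**Conclusion.** The point holds for scheduled SQ pairs. They give no overnight coverage, none timed to follow a meal and, after Adjustment, none before lunch or dinner. This follows from the schedule and the pair definition, without any assumption about ward times.

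Pooled MARD reaches the other hours systematically only through IV patients, so night accuracy is confounded with route. Each IV patient contributes about 5 to 6 times as many scheduled pairs as an SQ patient, assuming 3 to 10 days of wear and one route throughout. The share of the pool this represents depends on the number of IV patients, which the documents do not give.

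MARD remains a valid description of agreement at the times sampled. The gap lies in what it can be said to cover, and it can be closed in the analysis plan.

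**What to change.** In the Data Analysis Plan and Endpoints:

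- Report MARD and Bland-Altman agreement separately for SQ and IV patients.
- Within route, report by clock period: pre-breakfast, pre-lunch and pre-dinner, bedtime, and other or overnight.
- Classify each pair as scheduled or triggered, and show the two separately. Triggered pairs include alarm checks, rechecks, repeats after a discordant pair and the CGM-triggered hourly checks in IV patients. Show provider-requested checks as their own group.
- Base the SQ accuracy conclusion on scheduled pairs and limit it to the times sampled: all pre-meal and bedtime checks in Adjustment, pre-breakfast and bedtime in Utilization.

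This changes no check, dose or clinical rule. It costs some wording, a rule for classifying checks and a few tables. The downside is a narrower claim and small cells, so the split results should be read as descriptive.

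Laboratory glucose is at most an optional exploratory addition. The plan says "Different patient variables (demographics, comorbidities, labs and vitals, administered medications) will be collected from electronic health record", but it does not say that glucose draws with times are captured, and Aim 1 takes POC capillary glucose as its comparator.

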5. Nursing staff will compare AM and HS (before breakfast and at bedtime) POC glucometer reading to concomitant CGM reading to ensure readings remain accurate (within +/- 15% of each other). If CGM readings will fall outside this range, nursing will contact the research team for directions. The research team will recommend either to retest the accuracy of the sensor with POC glucometer, or to exchange the CGM sensor and then test the accuracy

The CGM will be set up with alarm limits of 85 for low glucose and 250 for high glucose. If these alarms are triggered, the nursing staff will take measures for these alarms as listed below. Treatment decisions will be made based on the POC glucometer reading as follows:

- For hypoglycemia alarm (BG<85mg/dl), POC glucometer will be used to confirm the glucose level. Measures will be taken to prevent or treat hypoglycemia.
 - If BG is 70-85mg/dl, patient will receive 15 gm of carbohydrates PO ASAP and blood glucose will be re-checked in 30 minutes.
 - If BG is <70, hypoglycemia protocol will be initiated. IV D50 pushes or IM glucagon will be used if patient is obtunded and unable to swallow. POC glucose will be re-checked in 15-30 minutes to ensure appropriate correction of hypoglycemia.
- For hyperglycemia (sustained BG>250) for more than 2 hours in a row, nursing staff will contact primary provider or inpatient endocrinology team for insulin dosing recommendations. POC glucose check will be obtained based on provider recommendations. Additional insulin will not be given between meals regardless of sensor reading unless otherwise recommended by attending physician or ARNP provider. Close attention will be given to avoid “insulin stacking phenomenon” and potential hypoglycemic events.

For patients receiving IV Insulin infusion:

Please note that during the entirety of the study while the patient is receiving IV insulin, the insulin infusion dose will only be adjusted using the POC BG readings. CGM data will only be used to monitor BG range and if BG is found to be outside of expected range, the POC glucose will be checked and insulin infusion will be adjusted based on the POC glucometer reading.

Adjustment Phase

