In the “Adjustment Phase”, during the first 12 hours, sensor accuracy will be assessed. Patients will continue to have their blood glucose (BG) checked with POC glucometer concomitant with CGM use. Nursing staff will check POC BG every 1 hour for the first 12 hours (as per established IV insulin infusion protocol). CGM readings will be recorded in chart at the same time as POC glucometer reading is obtained. These readings will be entered by nursing staff under the “comments” section of the MAR screen. The glucometer readings and CGM data at the time of glucometer readings will be compared by nursing staff. The CGM readings should not be either 15% higher or 15% lower than the corresponding POC glucometer reading. Should this CGM reading fall outside this range, a second reading will be done within 30 minutes and readings will be compared to reassess accuracy. After the patient has had sensor in place for 12 hours and at least 12 POC glucometer glucose checks have been recorded and compared against CGM values, the research team will be notified to determine if the frequency of POC checks can be safely decreased based on CGM accuracy.

If 12 comparison points – CGM readings and POC glucometer reading – are deemed accurate (within +/- 15% of each other for all 12 readings), then patient will enter the “Utilization Phase”.

If 2 or more consecutive CGM readings do not correlate with POC glucometer values, the research team will be notified. The research team will evaluate the data and decide if the sensor should be replaced and another 12-hour cycle of adjustment phase re-initiated or if patient participation should be terminated.

Utilization Phase

Once CGM accuracy has been established in the “Adjustment Phase” above, the frequency of POC glucose checks will be reduced as follows:

1. POC glucometer checks will be reduced to every 2 hours
2. CGM readings will continue to be recorded hourly by nursing staff.
 - a. If CGM glucose remains in range (140-180 mg/dl), the same insulin infusion rate will be continued.
 - b. If CGM glucose is out of range (<140 or >180) then nursing staff will resume POC glucose check every 1 hour. Insulin infusion will be adjusted as needed per IV insulin infusion protocol using the POC glucometer reading **only**.
3. If IV insulin infusion dose is adjusted, nursing staff will resume POC glucometer checks every 1 hour until the POC glucose remains in range for 2 consecutive readings

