4. Once BG remains within range for 2 consecutive POC glucometer readings, POC glucose checks will be again decreased to every 2 hours

5. If the patient is transitioned from IV insulin infusion to SQ insulin, the nursing staff will notify the research staff and will proceed to the SQ insulin protocol above. The alarms will be adjusted as described in the SQ insulin protocol.

The CGM will be set up with alarm limits of **Low Glucose (<140 mg/dl)**, **Urgent Low Glucose (<70)** and **High Glucose (>180)**. If these alarms are triggered, the nursing staff will perform a STAT POC glucose check to confirm blood glucose (BG) level. Treatment decisions will be made based on the POC glucometer reading as follows:

- For hypoglycemia:
 - If POC BG is between 85-140 mg/dl, hold IV insulin infusion and re-check POC glucose in 30 minutes
 - If POC BG is between 70-84 mg/dl, hold IV insulin and ask patient to take 15gm of carbohydrates PO ASAP and recheck POC glucose level in 30 minutes
 - If POC BG is < 70, apply hypoglycemia protocol. Hold IV insulin. Give IV D50 or IM glucagon to obtunded patients. Give PO carbohydrates to alert, able to swallow patients. Repeat POC glucose level in 15 min. and 30 min.
 - Continue to check POC blood glucose every 1 hour until glucose remains in range (140-180 mg/dl) for 2 consecutive readings.
 - Once BG remains within range for 2 consecutive POC glucometer readings, POC glucose checks will be decreased to every 2 hours
- For hyperglycemia (BG>180):
 - Check glucose level using POC glucometer and adjust IV insulin infusion rate accordingly
 - Continue checking POC glucose every 1 hour until glucose remains in range (140-180 mg/dl) for 2 consecutive readings
 - Once BG remains within range for 2 consecutive POC glucometer readings, POC glucose checks will be decreased to every 2 hours

Methods (continued):

Treatment of the DM and associated complications, dosing of the insulin, change from PO to insulin treatment and back to PO medications during hospitalization or at discharge will be guided by the admitting team with as needed help from the inpatient Endocrinology Consultation Service.

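### IV Utilization drops the ±15% CGM-POC agreement check that SQ Utilization keeps, so a drifting sensor that still displays 140-180 mg/dl has no stated retest or exchange

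*Combined protocol and SAP*

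**What the plan says.** All references are to Study Design and Methods, Methods, unless another section is named.

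**SQ insulin, Utilization Phase, item 5.** The agreement check continues: "Nursing staff will compare AM and HS (before breakfast and at bedtime) POC glucometer reading to concomitant CGM reading to ensure readings remain accurate", with ±15% as the limit. Outside it, nurses call the research team, and "The research team will recommend either to retest the accuracy of the sensor with POC glucometer, or to exchange the CGM sensor".

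**IV insulin, Adjustment Phase.** All 12 pairs must agree within ±15% before Utilization begins. A single discordant pair is repeated: "Should this CGM reading fall outside this range, a second reading will be done within 30 minutes and readings will be compared to reassess accuracy". Two or more consecutive discordant readings go to the research team, which may replace the sensor and restart the 12-hour cycle or end participation.

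**IV insulin, Utilization Phase.** POC falls to every 2 hours and CGM is charted hourly. Item 2a reads: "If CGM glucose remains in range (140-180 mg/dl), the same insulin infusion rate will be continued". Item 2b reads: "If CGM glucose is out of range (<140 or >180) then nursing staff will resume POC glucose check every 1 hour". Item 3 restores hourly POC after a dose change. Item 4 ends it: "Once BG remains within range for 2 consecutive POC glucometer readings, POC glucose checks will be again decreased to every 2 hours". Item 5 covers transition to SQ insulin.

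**IV safeguards.** Throughout, "the insulin infusion dose will only be adjusted using the POC BG readings". When a CGM alarm fires (below 140, below 70 or above 180), "the nursing staff will perform a STAT POC glucose check to confirm blood glucose (BG) level".

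**The concern.** Every IV Utilization trigger is a level or an event: the displayed CGM value, the POC value, a dose change or a change of insulin route. None is a disagreement between the two devices. If CGM is more than 15% away from POC but displays 140-180, item 2a applies and the sensor stays in use.

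The 2-hourly schedule is justified by accuracy shown in the first 12 hours. The Background names hypoxemia, hypoperfusion, intravenous drugs and fast-changing clinical status as threats to accuracy, and these can alter later. In alternate hours CGM is the only scheduled reading. After two in-range POC values, item 4 restores the 2-hourly schedule on the same sensor, even if that sensor now fails the plan's own 15% standard.

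Two things are not at issue. Insulin infusion is not dosed from CGM, and the disagreement is not hidden from the MARD, because the Data Analysis Plan takes matched pairs without restricting them to one phase.

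**Working it through.** The plan gives no figure on this point to reproduce. The check has three parts.

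**1. Do other rules fill the gap?**

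| Rule | SQ | IV |
|---|---|---|
| ±15% comparison in Adjustment | yes | yes |
| Consecutive-discordance rule in Adjustment | yes | yes |
| ±15% comparison in Utilization | yes (item 5) | none |
| Retest or exchange in Utilization | yes (item 5) | none |

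The IV consecutive-discordance rule sits under the Adjustment heading, and its sensor remedy is another 12-hour adjustment cycle. SQ Adjustment has a matching rule, yet SQ still adds item 5. Criteria for Discontinuation, item 3, covers only repeated CGM lows that the finger-stick does not support.

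**2. What can be masked?**

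Inputs: target band 140-180 mg/dl (40 mg/dl wide) and tolerance ±15%, both from the protocol. Bias b is an assumption, with CGM = POC × (1 + b). A display of 140-180 then means POC from 140/(1 + b) to 180/(1 + b).

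| b | POC displayed as 140-180 | POC with both devices in range | Share of band |
|---|---|---|---|
| +16% | 120.7-155.2 | 140-155.2 | 15.17/40 = 37.9% |
| +20% | 116.7-150.0 | 140-150 | 10/40 = 25% |
| -16% | 166.7-214.3 | 166.7-180 | 13.33/40 = 33.3% |
| -20% | 175.0-225.0 | 175-180 | 5/40 = 12.5% |

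These are shares of band width, not probabilities.

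- Masked low side at +20%: CGM 140-168 means POC 116.7-140.
- Masked high side at -20%: CGM 144-180 means POC 180-225.
- The both-in-range window closes at 180/140 - 1 = +28.6% and at 140/180 - 1 = -22.2%.
- Hiding POC below 85 needs a bias above 140/85 - 1 = 64.7%. Hiding POC below 70 needs more than 140/70 - 1 = 100%.
- Pairs available but not compared: 24/2 = 12 per day.
- Added delay: 2-hourly instead of hourly POC, so at most about 1 hour per excursion.

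**3. How often would a ±15% check prompt a repeat?**

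Assume normal relative error. The documents give no sensor SD, so a range is shown. Repeats per day = 12 × P(|error| > 15%).

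| Bias, SD | Pairs outside ±15% | Repeats per day |
|---|---|---|
| 0, 5% | 0.27% | 0.03 |
| 0, 8% | 6.1% | 0.73 |
| 0, 10% | 13.4% | 1.6 |
| 0, 12% | 21.1% | 2.5 |
| 10%, 5% | 15.9% | 1.9 |
| 15%, 5% | 50% | 6.0 |
| 20%, 5% | 84.1% | 10.1 if nothing were done |

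Confirmed failure per scheduled check at 20% bias, SD 5%: 0.841² = 0.708 if the two errors are independent, 0.841 if fully shared. That is 1/0.708 = 1.41 to 1/0.841 = 1.19 checks to confirmation.

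False confirmation at zero bias, SD 8%: 12 × 0.061² = 0.04 per day (independent) to 0.73 per day (fully shared).

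**The case against.** The strongest defence is that the two arms differ for a reason. SQ patients have lunch and dinner insulin dosed from CGM, only two scheduled POC checks a day, and alarms at 85 and 250. IV patients are dosed on POC alone, keep about 12 POC checks a day and have alarms at 140 and 180. SQ may well need the check more. That lowers the weight of the point but does not remove it, because in IV the CGM still justifies halving the POC frequency.

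The window is also narrow. At +20% bias, an in-range POC above 150 displays above 180 and brings a STAT POC and hourly checks. A POC outside the band that leads to a dose change restores hourly checks too. This stands, and it limits how long a sensor could go on undisturbed. But those rules respond to the glucose level, and none leads to a retest or exchange.

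A comparison at the scheduled POC would not find the first masked excursion sooner, since that same POC already reveals it. This also stands: the gain is in later excursions and in pairs that are both in range but discordant.

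The two nursing flow-sheets are not among the documents and might carry the check. That cannot be assumed; if they do, the protocol text only needs to match. The consecutive-discordance rule could be read as running through both phases, but its heading and remedy point to Adjustment. Shock and intubation are excluded at entry and, with ICU transfer, are grounds for stopping. Hypoxemia and intravenous drugs remain.

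Sensor SDs of 10-12% would raise the cost. Such sensors would seldom enter Utilization: with independent errors and no credit for repeat readings, all 12 pairs pass with probability (1 - 0.134)^12 = 0.18 and (1 - 0.211)^12 = 0.06.

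**Conclusion.** The concern holds and is minor. As written, an IV patient's sensor can fail the plan's own 15% criterion during Utilization, still display 140-180, and meet no instruction to retest or replace it. The likely harm is limited to values moderately outside the target band, such as POC 116.7-140 or 180-225 at 20% bias, found at most about 1 hour later than under hourly POC. Realistic drift does not mask hypoglycemia.

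The finding itself rests on the text alone. The sizes assume a constant proportional bias. Confidence in the gap is high as far as the protocol goes; the flow-sheets could not be checked.

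**What to change.** Add one item to IV Utilization, built from rules already in the plan:

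- At each scheduled POC check, compare it with the concurrent CGM reading.
- If they differ by more than 15%, repeat both within 30 minutes, as in IV Adjustment.
- If they still differ, go back to hourly POC and contact the research team to retest or exchange the sensor, as in SQ item 5.

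Put the same line on the IV flow-sheet. No new data item is needed, because CGM is already recorded hourly.

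The cost is a few finger-sticks. An unbiased sensor with SD 5-8% would prompt about 0.03-0.7 repeats per patient-day. After a confirmed failure, hourly POC adds up to 24 - 12 = 12 checks per day until the sensor is dealt with. An exchange means a 2-hour warm-up plus a 12-hour Adjustment cycle: 14 hourly checks instead of 7, so 7 extra if POC is hourly throughout. False confirmations would add some room entries. The measured reduction in POC use, a primary endpoint, would be slightly smaller.
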